8.3.1 Pathology

Survivin Expression Status

Over 85% of glioblastomas have survivin protein expression that is detectable by immunohistochemistry. A determination of survivin positivity by central pathology review is required for eligibility. All patients will have unstained slides or tissue blocks submitted to the central pathology core (Roswell Park Cancer Institute) for survivin testing.

A. Patients from Roswell Park Cancer Institute:

1. Unstained Slides:

- Send all slides within 6 weeks of cutting
- At least 24 unstained slides or one tissue block
- Precut slides from paraffin blocks in 5 micron sections
- Mount on Poly-L-Lysine-coated or plus (+) slides
- Air dry. Do not oven dry

• Store specimen at room temperature

B. Patients from Network Sites:

- 1. Unstained Slides:
 - Send all slides within 6 weeks of cutting
 - At least 24 unstained slides or one tissue block
 - Precut slides from paraffin blocks in 5 micron sections
 - Mount on Poly-L-Lysine-coated or plus (+) slides
 - Air dry. Do not oven dry
 - Store specimen at room temperature

While unstained slides are preferred, tissue blocks are acceptable. If tissue blocks are being sent instead of unstained slides, please follow the procedure below for processing and shipping.

Fixed Paraffin Block with Corresponding H&E:

- Tissue should be well-fixed in formalin. If alternative fixative is used, it should be noted on the requisition.
- 0.2 cm x 0.2 cm x 0.2 cm tissue
- Store specimen at room temperature.
- Use cold pack for transport. Be sure cold pack is not in direct contact with specimen during transport.

For Network Sites: Send samples, along with the sponsor-provided shipping log, using study-specific subject ID number and tissue accession number to RPCI Pathology Network Shared Resource (Attn: Protocol Lab Team). The shipping label should read as follows:

Roswell Park Cancer Institute
Correlative Sciences Pathology Office, S-636
Attn: Protocol Lab Team – I 259614 Samples
[name]
[name]
[contact]

Email: [contact]

Samples will be analyzed in RPCI's Pathology Network Shared Resource by [name] ([contact], [contact]).

Tissue will also be tested for Survivan, MGMT methylation status, IDH-1, and PDL-1 expression. MGMT and IDH-1 tests require 6 unstained slides for each test. Survivan and PDL-1 immunohistochemistry stains on tumor tissue each require 3 unstained slides. For evaluable patients only, OmniSeq Comprehensive and OmniSeq Immune Advance will also be tested. 3 unstained slides are required for each of these.

Unstained slides will be sent for the following tests:

Test	Slides required
Survivin	3 unstained slides
PDL-1	3 unstained slides
Omniseq Comprehensive	3 unstained slides
Omniseq Immune Advance	3 unstained slides
IDH-1	6 unstained slides
MGMT methylation	6 unstained slides

9 EFFICACY EVALUATIONS

9.1 Objective Tumor Response

All protocol-defined imaging studies must be performed at the investigative site or sponsor-approved facility using protocol-defined parameters. The same method of assessment and the same technique should be used to characterize each identified and reported lesion at baseline and during follow-up. The Modified Response Assessment in Neuro-Oncology (RANO) Response Criteria (**Appendix C**) will be used to define tumor response and progression (40).

It is important to use the same method of assessment from one scan to the subsequent scans.

Rarely, patients undergoing vaccine therapy for tumor can develop an inflammatory response in the tumor bed that mimics either true tumor recurrence or pseudoprogression. If a patient who has completed the 4-dose vaccine priming phase of treatment undergoes either biopsy or re-resection of new contrast-enhancing tissue and no tumor is determined by the local neuropathologist to be present on histologic exam, the patient may continue on treatment under

protocol with approval of the lead principal investigator. If any amount of tumor is found to be present at re-biopsy, the patient must be declared to have progressed as of the date of the MRI scan that first showed the new enhancement. Patients with new enhancement during the priming phase that is not suspected to be pseudoprogression are not eligible to continue treatment on protocol.

9.2 Evaluation of Response

The largest cross-sectional area on the T1-weighted contrast-enhanced images will be selected and measured in 2 dimensions with linear measures on the baseline MRI axial sequence. In addition, the largest cross-sectional area of a contiguous hyperintense lesion on FLAIR sequences will be measured on the baseline MRI axial sequence. If there is no enhancement on the baseline MRI done with 72 hours post-op, this should be noted as no evidence of disease (NED). All subsequent scans will be compared against these baseline measures (for both CE and FLAIR). New foci of FLAIR signal abnormality will be recorded on each subsequent evaluation. Response will be scored based on a combination of imaging and clinical features as defined by the modified RANO criteria (40). Objective response rate is defined as the sum of partial responses plus complete responses.

For the purpose of treatment decisions, progression will be assessed by the treating investigator. 20% to 30% of patients who receive chemoradiotherapy for newly diagnosed glioblastoma can exhibit transient increase in tumor enhancement that eventually subsides without change in therapy (pseudoprogression) (40). The protocol allows for investigators to confirm progression before removal of patients from study treatment, thus ensuring radiographic follow-up to a valid disease progression time point. In every case when there is doubt about progression versus "pseudoprogression", use of perfusion and diffusion weighted imaging is encouraged. Patients may continue on treatment and remain under close observation and evaluation at four-week intervals if there is uncertainty regarding whether apparent radiographic progression may represent "pseudoprogression" and the patient is doing well clinically or is clinically stable. If subsequent evaluations indicate that the patient is in fact experiencing progression, then the date of progression should be the time point at which this issue was first raised.

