9.2.1 Survival

Duration of survival will be defined as the time from date of diagnosis to death due to any cause.

In all cases, progression-free survival will be assessed using the RANO response criteria for GBM which considers radiologic imaging, neurological status, and steroid dosing. According to these criteria, progression of disease will be assumed if any of the following criteria are met:

• ≥25% increase in the sum of the products of perpendicular diameters of enhancing lesions compared with baseline (post-chemoradiation) or best response after initiation of therapy.

NOTE: Due to the fact that little to no residual disease will be present at baseline in these patients, a 25% increase in area could easily reflect only imaging variance. Therefore, in order to be considered progressive disease, a > 5 mm increase in maximal diameter, as well as $\ge 25\%$

increase in the sum of the products of the progressing lesions will be required to assign a status of progressive disease.

- Significant increase in T2/FLAIR non-enhancing lesion compared with baseline (post-chemoradiation) or best response after initiation of therapy, not caused by comorbid events (e.g., radiation therapy, demyelination, ischemic injury, infection, seizures, postoperative changes, or other treatment effects).
- Clear progression of non-measurable disease.
- Any new lesion.

NOTE: Patients may continue on treatment and remain under close observation and evaluation at four-week intervals if there is uncertainty regarding whether apparent radiographic progression may represent "pseudoprogression". If subsequent evaluations suggest that the patient is in fact experiencing progression, then the date of progression should be the time point at which this issue was first raised. Similarly, stable disease may be assigned in cases of presumed "pseudoprogression" associated with decreased steroid use.

- Clear clinical deterioration not attributable to other causes apart from the tumor (e.g., seizures, medication adverse effects, complications of therapy, cerebrovascular events, infection, and so on) or changes in corticosteroid dose
- Failure to return for evaluation as a result of death or deteriorating condition

NOTE: Any cystic or surgical cavity should not be measured in determining response. At baseline, tumor around the surgical cavity should generally be considered nonmeasurable unless there is a nodular component measuring 10 mm in diameter.

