Appendix C Response Assessment in Neuro-Oncology (RANO)

Response	T1 Contrast Enhancement (CE)	FLAIR Images	Steroids	Neurologic Exam
Complete Response (CR)	No residual CE (complete disappearance of all enhancing measurable disease for at least 4 weeks; confirmatory MRI at 4 weeks is required to score as CR) and no new lesions.	Stable or reduced area of FLAIR signal abnormality	No steroids	Stable or improved from prior evaluation
Partial Response (PR)	>50% reduction in sum of products of the perpendicular diameters of all measureable enhancing lesions sustained for at least 4 weeks and no new lesions or progression of non-measurable lesions.	Stable or reduced area of FLAIR signal abnormality	Stable or reduced glucocorticoids from baseline MRI	Stable or improved from prior evaluation
Minor response (MR)	>25% reduction in sum of products of the perpendicular diameters of all measureable enhancing lesions and no new lesions (confirmatory MRI at 4 weeks is required to score as PR).	Stable or reduced area of FLAIR signal abnormality	Stable or reduced glucocorticoids from baseline MRI	Stable or improved from prior evaluation
Stable Disease (SD)	<25% reduction in area of CE maintained for at least 4 weeks duration. Does not qualify for CR, PR or progression.	Stable or reduced area of FLAIR signal abnormality	Stable or reduced glucocorticoids from baseline MRI	Stable or improved from prior evaluation
Progressive Disease	>25% in the sum of products of the perpendicular diameters of CE lesions; evidence of new lesion(s).	Measurable increase in the sum of products of the perpendicular diameters of FLAIR signal abnormality from the baseline scan or the scan representing the best response (if there was a response) following therapy and not attributable to other comorbid events (seizure, radiation, injury, infection, ischemia, etc.) OR presence of a new focus of FLAIR signal abnormality that cannot be explained by any other pathologic process.	Stable or increased dose of glucocorticoids	Stable or worsening neurologic symptoms

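### Section 9.2 takes the post-operative MRI as baseline for all later scans, which is inconsistent with the post-chemoradiation baseline that Section 9.2.1 sets for PFS progression

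*Combined protocol and SAP*

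**What the plan says.** Section 9.2 (Evaluation of Response) has enhancing and FLAIR lesions measured on the baseline MRI. It identifies that scan in the next step: "If there is no enhancement on the baseline MRI done with 72 hours post-op", then "this should be noted as no evidence of disease (NED"). The comparison rule follows: "All subsequent scans will be compared against these baseline measures (for both CE and FLAIR").

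Section 9.2.1 (Survival) introduces its progression list as the rule for assessing PFS in every case. For enhancing disease the reference is "enhancing lesions compared with baseline (post-chemoradiation) or best response after initiation of therapy". The T2/FLAIR item names the same reference. A note adds a size condition: the largest diameter must grow by more than 5 mm as well as the area by at least 25%.

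Section 9.1 says that the RANO criteria in Appendix C "will be used to define tumor response and progression". In the progressive-disease row of Appendix C, the FLAIR entry measures change "from the baseline scan or the scan representing the best response" and does not say which scan is the baseline. The contrast-enhancement entry gives a threshold above 25% and names no reference scan.

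The two candidate baselines are separate examinations, and Table 3 footnote 10 requires both.

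**The concern.** PFS6 is the primary endpoint, and a progression call depends on the scan used for comparison. Six weeks of chemoradiation separate the two candidate scans, and Section 9.2 itself notes that "20% to 30% of patients who receive chemoradiotherapy for newly diagnosed glioblastoma can exhibit transient increase in tumor enhancement". Criterion 10 in Section 5.1 admits patients whose enhancement is new or larger after chemoradiation if the investigator thinks pseudoprogression likely. In those patients the two scans differ by construction.

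Read literally, Section 9.2 carries the growth that occurred before the first vaccine dose into every later comparison. A patient could then meet a progression threshold on the entry scan. The dating rule in Sections 9.2 and 9.2.1 adds to this, because accepted progression is dated to when the question first arose. Against a post-operative reference that could be the entry scan, at the earliest about 10 weeks after surgery (about 4 weeks of recovery plus 6 weeks of chemoradiation, Section 4.1). The same images could be a PFS6 failure at one site and event-free at another.

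**Working it through.** The plan gives no figure on this point to reproduce. The check compares the texts and then works one example.

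**Which scan is the baseline**

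| Place | Reference scan |
|---|---|
| Section 9.2 | Post-operative MRI (72 hours), for enhancement and FLAIR |
| Section 9.2.1 | Post-chemoradiation MRI or best response, for enhancement and T2/FLAIR |
| Appendix C | Baseline scan, not defined; none named for enhancement |
| Section 4.1 | Screening assessments other than HLA and survivin testing come after chemoradiation, which agrees with 9.2.1 |

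**Whether 9.2 can be confined to response.** Its comparison rule covers all later scans, and its second paragraph deals with judging and dating progression. A post-operative reference does not suit response either. Sections 3.2, 12.2 and 12.7.1 restrict objective response to patients with evaluable disease when they enter the study, and criterion 13 places entry after chemoradiation. A patient with no enhancement after surgery but measurable enhancement at entry has no post-operative area from which to calculate a percentage reduction.

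**Worked example with assumed lesion sizes.** The post-operative lesion is 10x10 mm, the criterion 9 limit of 100 mm². The entry (post-chemoradiation) lesion is 16x16 mm and the later one 17x17 mm. All are at least 10 mm, so the Section 9.2.1 note that tumour around the cavity "should generally be considered nonmeasurable unless there is a nodular component measuring 10 mm in diameter" does not decide the case.

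Area change = (later side² / reference side²) − 1. Diameter change = later side − reference side.

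- Entry against post-operative: 256/100 − 1 = +156%; 16 − 10 = +6 mm. Both size conditions of 9.2.1 are met before any vaccine.
- Later against post-operative: 289/100 − 1 = +189%; 17 − 10 = +7 mm. Met.
- Later against post-chemoradiation: 289/256 − 1 = +13%; 17 − 16 = +1 mm. Not met.

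From 10x10 mm after surgery, any square lesion above 15x15 mm at entry meets both conditions against the post-operative scan, since 15²/10² − 1 = +125% and the gain then exceeds 5 mm.

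The contrast does not depend on the 5 mm note. On the Appendix C area threshold alone (above 25%), +189% exceeds it and +13% does not.

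**The case against.** The strongest reply is that Section 9.2.1 already settles the matter for PFS. It applies to PFS in every case and names the post-chemoradiation scan for both lesion types, and Section 4.1 agrees with it. Section 9.2 is headed as response evaluation, its comparison rule is followed directly by response scoring, and its progression paragraph opens with treatment decisions. The 72-hour wording appears only in a conditional sentence about recording no evidence of disease. Section 9.2 also has no progression threshold of its own, so the example joins its baseline to a threshold stated elsewhere. Finally, both sections let patients with uncertain progression continue under four-week review, and 9.2.1 allows stable disease to be assigned when presumed pseudoprogression goes with decreasing steroid use.

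Much of this stands. Section 9.2.1 is the controlling text for the primary endpoint, and a careful site would follow it. It is therefore right to say that sites could score differently, not that they would. The borrowed threshold is a fair criticism, although Section 9.1 sends the reader to Appendix C for thresholds, and Appendix C does not identify the baseline scan.

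Three things remain. The conditional sentence still identifies which MRI is the baseline. The response-only reading is not stated, and it would leave the wrong reference for response. The pseudoprogression allowances are discretionary and do not change the reference scan.

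**Conclusion.** The point holds as an internal inconsistency that should be corrected. Section 9.2 states a baseline that conflicts with Section 9.2.1 and does not fit objective response, and Appendix C does not resolve the conflict. The patients exposed are those admitted under criterion 10 with new or greater enhancement, for whom the choice of scan can reverse the classification. The lesion sizes that show this are assumed.

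A reader might infer that the primary endpoint is undefined or that PFS6 will be biased. The documents do not support either reading. Section 9.2.1 gives a usable PFS rule, and nothing shows that any site applied the post-operative reference. A reader might also turn the 20% to 30% pseudoprogression figure into 10 to 15 of the 50 evaluable patients (0.20 × 50 and 0.30 × 50). That is context only. The plan does not say how many such patients have visible enhancement at entry, or how many would still exceed a threshold later.

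The direction of any effect is also unknown, because Section 12.7.1 does not state the reference scan behind the historical PFS6 of 0.55.

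**What to change.** In Section 9.2, replace the 72-hour post-operative baseline with the last post-chemoradiation MRI before the first vaccine dose. In Section 9.2 and Appendix C, state that this scan is the baseline for response, and that this scan or the best response since is the reference for progression, for both enhancement and FLAIR. Keep the post-operative MRI for inclusion criteria 9 and 10.

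The change is to wording. Both scans are already required, so no imaging is added, and dosing does not change. There are two costs. Any scans already scored against the post-operative MRI would need rescoring. True progression mistaken for pseudoprogression at entry would be absorbed into the baseline, a consequence that Section 9.2.1 already implies.

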9.2.1 Survival

Duration of survival will be defined as the time from date of diagnosis to death due to any cause.

In all cases, progression-free survival will be assessed using the RANO response criteria for GBM which considers radiologic imaging, neurological status, and steroid dosing. According to these criteria, progression of disease will be assumed if any of the following criteria are met:

• ≥25% increase in the sum of the products of perpendicular diameters of enhancing lesions compared with baseline (post-chemoradiation) or best response after initiation of therapy.

NOTE: Due to the fact that little to no residual disease will be present at baseline in these patients, a 25% increase in area could easily reflect only imaging variance. Therefore, in order to be considered progressive disease, a > 5 mm increase in maximal diameter, as well as $\ge 25\%$

increase in the sum of the products of the progressing lesions will be required to assign a status of progressive disease.

- Significant increase in T2/FLAIR non-enhancing lesion compared with baseline (post-chemoradiation) or best response after initiation of therapy, not caused by comorbid events (e.g., radiation therapy, demyelination, ischemic injury, infection, seizures, postoperative changes, or other treatment effects).
- Clear progression of non-measurable disease.
- Any new lesion.

NOTE: Patients may continue on treatment and remain under close observation and evaluation at four-week intervals if there is uncertainty regarding whether apparent radiographic progression may represent "pseudoprogression". If subsequent evaluations suggest that the patient is in fact experiencing progression, then the date of progression should be the time point at which this issue was first raised. Similarly, stable disease may be assigned in cases of presumed "pseudoprogression" associated with decreased steroid use.

- Clear clinical deterioration not attributable to other causes apart from the tumor (e.g., seizures, medication adverse effects, complications of therapy, cerebrovascular events, infection, and so on) or changes in corticosteroid dose
- Failure to return for evaluation as a result of death or deteriorating condition

NOTE: Any cystic or surgical cavity should not be measured in determining response. At baseline, tumor around the surgical cavity should generally be considered nonmeasurable unless there is a nodular component measuring 10 mm in diameter.

10 SAFETY EVALUATION

10.1 Adverse Events

10.1.1 Definition

An adverse event or adverse experience (AE) is any untoward medical occurrence associated with the use of a drug in humans, whether or not considered drug related. Therefore, an AE can be ANY unfavorable and unintended sign (including an abnormal laboratory finding), symptom, or disease temporally associated with the use of a medicinal (investigational) product, whether or not considered related to the medicinal (investigational) product (attribution of 'unrelated', 'unlikely', 'possible', 'probable', or 'definite').

An AE is considered "unexpected" if it is not listed in the investigator brochure or is not listed at the specificity or severity that has been observed; or if an investigator brochure is not required or available, is not consistent with the risk information described in the general investigational plan in other study-related documents.

10.1.1.1 Diagnosis Versus Signs and Symptoms

If known, a diagnosis should be recorded on the CRF rather than individual signs and symptoms (e.g., record only liver failure or hepatitis rather than jaundice, asterixis, and elevated transaminases). However, if a constellation of signs and/or symptoms cannot be clinically characterized as a single diagnosis or syndrome at the time of reporting, each individual event should be recorded as an AE or SAE on the CRF. If a diagnosis is subsequently established, it should be reported as follow-up information.

10.1.1.2 Adverse Events Occurring Secondary to Other Events

In general, AEs occurring secondary to other events (e.g., cascade events or clinical sequelae) should be identified by their primary cause. For example, if severe diarrhea is known to have resulted in dehydration, it is sufficient to record only diarrhea as an AE or SAE on the CRF.

However, clinically significant AEs occurring secondary to an initiating event that are separated in time should be recorded as independent events on the CRF. For example, if a severe gastrointestinal hemorrhage leads to renal failure, both events should be recorded separately on the CRF.

10.1.1.3 Abnormal Laboratory Values

Only clinically significant laboratory abnormalities that require active management will be recorded as AEs or SAEs on the CRF (e.g., abnormalities that require study drug dose modification, discontinuation of study treatment, more frequent follow-up assessments, further diagnostic investigation, etc.).

If the clinically significant laboratory abnormality is a sign of a disease or syndrome (e.g., alkaline phosphatase and bilirubin 5 x the upper limit of normal associated with cholecystitis), only the diagnosis (e.g., cholecystitis) needs to be recorded on the Adverse Event CRF.

If the clinically significant laboratory abnormality is not a sign of a disease or syndrome, the abnormality itself should be recorded as an AE or SAE on the CRF. If the laboratory abnormality can be characterized by a precise clinical term, the clinical term should be recorded as the AE or SAE. For example, an elevated serum potassium level of 7 mEq/L should be recorded as "hyperkalemia"

Observations of the same clinically significant laboratory abnormality from visit to visit should not be repeatedly recorded as AEs or SAEs on the CRF, unless their severity, seriousness, or etiology changes.

The following clinical laboratory tests will be performed during this study to assess safety (see Schedule of Procedures and Observations: **Table 3**, for specific tests):

- Hematology
- Serum Chemistries
- Urinalysis

The following evaluations will also be performed during the study to measure the safety and tolerability of study treatment:

- Vital sign measurements
- Physical examination
- Neurological examination
- Karnofsky Performance Status

